6.0 Study Flow

6.1 Study Design

This study is a randomized single-blind clinical trial and followed the Consolidated Standards of Reporting Trials (CONSORT) statement.

Each participant received only one composite restoration and the participants were blinded to the type of preparation technique used. The study dentist who completed the restoration was not blinded to the preparation technique because the form (shape) of the two types of preparations is distinctly different. However, the restoration evaluators will be blinded to the preparation design.

A HIPAA-compliant and browser-based electronic capture software, REDCap, was used for consent taking and research data recording and storage, including intraoral digital photographs. All data remained within REDCap and access was restricted to authorized personnel only. OCT scans were de-identified prior to uploading into BOX storage and linked to data in REDCap through study participant ID.

6.2 Screening Procedures

A UMN CTSI data pull, housed in a data shelter, was generated as a random query. A preliminary data screening was conducted by the PI using the random order provided and a preliminary list of patients that satisfy the Patient- and Tooth-level inclusion criteria was created. The patients were contacted via telephone to invite them to be a part of the study. If interested, a telemeeting was scheduled with a trained team member.

The telemeetings were conducted via Zoom and study information was shared with the potential participants using Microsoft PowerPoint slides and any arising questions arising were answered. For participants who did not have access to the internet or were able to devise access, they were called on a phone line. At the end of this telemeeting, an in-person screening appointment was scheduled for interested participants, and a packet containing the combined consent/HIPAA form, Guidelines and Consent for Unsecured Email Correspondence for Research Participants, and the study instruction sheet were mailed to them either physically or electronically.

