9.0 Data Analysis

9.1 Power Analysis:

Sample size calculation was based on the clinical success rate of posterior class I composite restoration observed in a previous study [16]. Using a significance level of 0.05, power of 80%, and equivalence limit of 15%, the sample size required was 10 restorations per group. However, as the restorative technique of this study is different from the previous study [16], the number of restorations was increased to 15 per group and to account for potential dropouts, the sample size was further increased to 18 per group.

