9.2 Statistical Analysis

Descriptive analysis of the FDI criteria, USPHS criteria and OCT outcome measure for marginal defects for each group was performed.

For comparison between groups with FDI and USPHS criteria, the Mann-Whitney test was used, all with alpha = 0.05.

For comparison between groups with OCT outcome measure, the Shapiro-Wilk test was used to determine the distribution of the data and it was found the data was not normally distributed. Hence the non-parametric Mann-Whitney test was used to compare the prevalence of the three OCT outcome measures of the two groups.

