10.0 Results

10.1 Descriptive

Thirty-six restorations were placed in premolars and molars. In total, 2 recalls (6-months 18 - months) were performed after baseline assessment. There were 3 dropouts at the 6 months follow up yielding a dropout rate of 8.3%. Reasons for dropping out was moving to another city.

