10.4 Patterns of OCT reflectance at the cavosurface angle and tooth-restoration interface. (Secondary Outcome Measure 1 - 3) at baseline.

Group	Elevated OCT reflectance at cavosurface angle	Elevated OCT reflectance at Tooth-Restoration Interface	Diminished OCT reflectance at the tooth- restoration interface
1	6.75 ± 6.36	16.20 ± 4.85	14.44 ± 4.36
2	1.56 ± 8.64	7.44 ± 5.29	18.75 ± 4.29

Table 7 – Percentage of the perimeter of the restorations at baseline, presenting with the following three patterns of OCT reflectance.

Mann-Whitney tests showed that there were significantly more (P < 0.05) elevated OCT reflectance at cavosurface angle and elevated OCT reflectance at tooth-testoration Interface debonding at the margins of the restorations in Group 1 compared to those in Group 2. There were no significant difference of the diminished OCT reflectance at the tooth-restoration interface of gaps between Group 1 and 2.

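### Table 7 leaves ± and n undefined, and its entry 1.56 ± 8.64 cannot be a mean with SD, SE or 95% CI half-width for 18 restorations

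*Combined protocol and SAP*

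**What the plan says.** The caption of Table 7 in Section 10.4 describes the entries as "Percentage of the perimeter of the restorations at baseline, presenting with the following three patterns of OCT reflectance". Each of the six cells has the form x ± y:

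| Group | Elevated, cavosurface | Elevated, interface | Diminished, interface |
|---|---|---|---|
| 1 | 6.75 ± 6.36 | 16.20 ± 4.85 | 14.44 ± 4.36 |
| 2 | 1.56 ± 8.64 | 7.44 ± 5.29 | 18.75 ± 4.29 |

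Neither caption nor text says what ± denotes. Unlike Tables 3 and 6, Table 7 has no column for n.

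The text below it reports: "Mann-Whitney tests showed that there were significantly more (P < 0.05) elevated OCT reflectance at cavosurface angle". It says the same of elevated reflectance at the interface. For the third measure it says: "There were no significant difference of the diminished OCT reflectance at the tooth-restoration interface of gaps between Group 1 and 2". The only p value information is the threshold for the first two.

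Section 9.2 states that the "Shapiro-Wilk test was used to determine the distribution of the data and it was found the data was not normally distributed", and that the "non-parametric Mann-Whitney test was used to compare the prevalence of the three OCT outcome measures of the two groups". It names no summary statistic for the OCT data.

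On numbers, Section 6.1 says "Each participant received only one composite restoration", Section 10.1 says "Thirty-six restorations were placed in premolars and molars", and Section 9.1 says "the sample size was further increased to 18 per group". Tables 3 and 6 list 18 participants per group at baseline.

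**The concern.** A percentage of perimeter cannot be negative, and for non-negative values a small mean limits how large the spread can be. A spread of 8.64 beside a central value of 1.56 looks too large for a group of 18.

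The diminished-reflectance column raises a second, weaker question. Read as mean ± SD, the two groups differ by about one SD, yet the comparison is reported as not significant.

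Table 7 holds the only between-group differences that the document calls statistically significant. Marginal staining was not tested because no restoration showed any, and marginal irregularities showed no significant difference. A reader who wants to rely on the OCT signal cannot tell what the six entries are, how many restorations they summarise, or whether the cavosurface cell is correct.

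**Working it through.** **Inputs.** Group 2 cavosurface, 1.56 ± 8.64, and the other five cells (Table 7). Values are at least 0, being percentages of perimeter (Table 7 caption). There is one restoration per participant (Section 6.1), 36 in all (Section 10.1), 18 per group at baseline (Tables 3 and 6). That Table 7 uses all 18 per group, with the restoration as the unit, is an assumption; the table does not say so.

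**Step 1: can 1.56 ± 8.64 be a mean with a spread or precision measure?** For n non-negative values with mean m, the sample SD is largest when all values but one are zero. That maximum is m × √n.

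- *SD:* 1.56 × √18 = 1.56 × 4.243 = 6.62. If the mean was rounded down from 1.565, the limit is 6.64. Both are below 8.64. An SD of 8.64 needs n ≥ (8.64 / 1.56)² = 30.7, so at least 31 values in the group.
- *SE:* the maximum is m × √n / √n = m = 1.56, at any n.
- *95% CI half-width:* the maximum is t(0.975, 17) × m = 2.110 × 1.56 = 3.29.

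The entry fits none of the three. If fewer than 18 restorations were scanned, the SD limit falls further (for example 1.56 × √16 = 6.24).

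**Step 2: can it be a median with a spread measure?** Yes. Take 18 values: six zeros, then 0.5, 1.0, 1.5, 1.62, 3, 5, 8.64, 8.64, 9, 12, 15, 20. The median is (1.5 + 1.62) / 2 = 1.56, the lower quartile 0 and the upper quartile 8.64, so the IQR is 8.64.

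**Step 3: is the diminished-reflectance verdict plausible if the table is mean ± SD?** With n = 18 per group:

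- Difference: 18.75 − 14.44 = 4.31.
- Its standard error: √((4.36² + 4.29²) / 18) = √(37.41 / 18) = 1.44.
- Welch t = 4.31 / 1.44 = 2.99, p = 0.005.

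The trial used Mann-Whitney, so this is only a plausibility check. Simulated groups of 18, rescaled to the printed means and SDs (2,000 draws for each pair of distribution shapes), gave Mann-Whitney p > 0.05 in at most 0.05% of samples when both groups had the same shape. The share rose to about 9% when the shapes differed. One data set with oppositely skewed groups and the printed means and SDs gave p = 0.32. The verdict is therefore unlikely under mean ± SD but not impossible.

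The same test on the elevated-interface column gives (16.20 − 7.44) / √((4.85² + 5.29²) / 18) = 8.76 / 1.69 = 5.18, p = 0.00001, which agrees with the text. No such check is informative for the cavosurface column, because its Group 2 spread is the value in doubt.

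**Step 4: can all three verdicts hold under a median reading?** Yes. Constructed sets of 18 with exactly the printed medians and IQRs gave Mann-Whitney p = 0.030 (cavosurface), 0.00001 (elevated interface) and 0.085 (diminished), matching the text on all three.

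**The case against.** **The cell may be a reading error.** The text reviewed was extracted from a PDF by a program, and row labels in Tables 3 and 6 are visibly garbled. One misread digit in 1.56 or 8.64 could create the conflict. This stands as a caveat. The cell itself is cleanly formed and the other five read normally, but the PDF should be checked before anything else. The missing definition of ±, n, unit and exact p does not depend on it.

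**The entries may be medians.** Section 9.2 calls the data non-normal and uses a rank test, so medians would be natural. This also stands: Steps 2 and 4 show that the cell and all three verdicts are then possible. The defect would be one of labelling.

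**The unit may not be the restoration.** With 31 or more images or sites per group, mean ± SD would become possible. The caption and the one-restoration design point the other way, and no such unit is described, but it is not excluded. An unconventional mean ± range is not excluded either.

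**What a reader might wrongly infer.** It is tempting to conclude that the statement of no significant difference in diminished reflectance is false. The documents do not support that. The Welch p value rests on an unconfirmed mean ± SD reading and on a different test from the one used, and the verdict can hold under a median reading. Nor do they establish that the cavosurface cell is a misprint: that is one of several open explanations.

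**Conclusion.** The point holds in a limited form. As extracted, 1.56 ± 8.64 is incompatible with mean ± SD, mean ± SE and mean ± 95% CI half-width, given non-negative values and 18 restorations per group. The printed 8.64 compares with maxima of 6.62, 1.56 and 3.29. Confidence in this is high. So either the cell is wrong, or the entries are another statistic, or the unit is something else. The documents do not show which, and no corrected figure can be derived from them.

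The tension in the diminished-reflectance column applies only if the table is mean ± SD. Confidence about any of the three verdicts is moderate at best, and none is shown to be wrong.

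These are secondary outcomes at baseline, and no primary result changes. If the table proves to be mean ± SD, a reported OCT conclusion could change on re-running. If it is median-based and correct, only the labelling is missing.

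**What to change.** 1. Compare the Group 2 cavosurface cell with the source PDF, then with the restoration-level data, and correct it if it is wrong.
2. Re-run the three Mann-Whitney tests on those data.
3. In Table 7, state n per group, the unit of analysis and what each number is. Median and IQR suit data that the plan itself calls non-normal.
4. Give the exact p value for each measure.
5. Revise the sentences under the table only if the re-run tests require it.

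The cost is one table re-run on existing data, a footnote, and possibly a changed sentence. No new data are needed.
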